- B. **Study Type and Design:** This study is a randomized controlled trial pilot that will occur over an 18-week period. Participants will be recruited from local community health clinics and screened for A1C over 7.0% and clinical health measures (based on medical chart review), readability, Internet access, and cognitive impairment. Participants will be randomized into either the traditional DECIDE group (control) or the *eDECIDE* group (intervention). Traditional DECIDE consists of the regular 18-week in-person group sessions led by the candidate, as facilitator. The *eDECIDE* group sessions will consist of the newly translated online method. To assess problem-solving, diabetes self-care behaviors, diabetes and CVD knowledge, and dietary habits, participants will be administered the validated instruments listed in Table 5 at baseline, post-intervention, then at 3-month follow-up. Once participants are screened and randomized, they will be enrolled in the web-based program or the traditionally based program and complete a total of 18 weekly sessions. For *eDECIDE*, participants will have access to the weekly curriculum through a password-protected, interactive website. Participants in the intervention group will be asked to input their HbA1c number on the *eDECIDE* website. They will also be asked to create a unique username and password to login and use the *eDECIDE* website. All stored data will be secure and encrypted. Website is in development. Participants will be prompted to complete their workbook pages and answer any problems about barriers for the week. After prompting, participants will have the opportunity to submit their

completed workbook homework to their personal health coach (PI: [name]). Homework and sessions will be delivered through an eLearning system accessible through the eDECIDE website. Participants retrieve feedback via the website when logging back into their account. The personal health coach will not deliver problem-solving content. All content is scripted on the website and eLearning portal. Each week for 18 weeks, participants are asked to log on at least once for a total of 1 hour to complete the bi-weekly problem-solving training for that week. The training would include completing workbook pages and submitting responses to the coach. Participants in both groups will receive \$75 in gift cards (\$15 at first session, \$20 at completion of the 18 weeks, then \$20 at 3-month follow-up).

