1. **Blinding Procedures:** This study will not involve blinding (masking). Participants and research staff will be aware of random group assignment.
2. **Subject Enrollment:** The primary outcome of interest is HbA1c measurement in the traditional DECIDE (control) group and eDECIDE (intervention) group. A .5% change in HbA1c has been considered clinically meaningful. The standard deviation in both arms is assumed to be 1.3%.⁶¹ Based on 2 sample t-test, assuming type I error rate of 5%, and attrition rate of 20%, with 35 participants in

each group, the study is powered at 80% to detect a change in HbA1c level of at least 1% between the 2 groups.²⁴⁻²⁵ Hill-Briggs' intervention was successful in detecting HbA1c change of at least 1% in a previous study.²⁴⁻²⁵ We will recruit 100 participants allowing for attrition to reach our goal of 70 for the pilot RCT. Block randomization with block size of 10 will be employed. Within each block 5 participants will be assigned at random to control and 5 to intervention group using computer derived labels.

D. Subject Criteria (See Vulnerable Populations appendix, if applicable): While uncontrolled diabetes affects more than one racial/ethnic group, our study will focus on African American adults because the burden of disease and consequent health complications is greatest among this population, particularly in the state of Kansas. Here, African Americans have the highest diabetes prevalence (15.7%) compared to 8.7% for non-Hispanic whites. In Sedgwick County (the county in which KUSM-W is located), African Americans make up 9% of the population, but have the highest prevalence of diagnosed diabetes within the county at 15%, with Non-Hispanic whites at 8.1%.⁵⁴ This study will take place in our local community where improvements and innovations in access to diabetes self-management services are greatly needed. Examining multiple racial/ethnic groups is beyond the scope of the current application. Our intent is to determine the efficacy of eDECIDE with a focus on our most at-risk group (i.e., African Americans). Future studies will allow the resources and time to expand the study population beyond African Americans.

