2. **Study Procedures:** Participants will be randomized into either the traditional DECIDE group (control) or the eDECIDE group (intervention). Traditional DECIDE consists of the regular 9 in-person group sessions delivered bi-weekly. The eDECIDE group sessions will consist of the newly translated online method. To assess problem-solving, diabetes self-care behaviors, diabetes and CVD knowledge, and dietary habits, participants will be administered the validated instruments at baseline, post-intervention, then at 3-month follow-up. Once participants are screened and randomized, they will be enrolled in the web-based program or the traditionally based program and complete a total of 18 weekly sessions. For eDECIDE, participants will have access to the weekly curriculum through a password-protected, interactive website. Participants will be prompted to complete their workbook pages and answer any problems about barriers for the week. After prompting, participants will have the opportunity to submit their completed workbook homework to their personal health coach (who will be hired for the RCT and work closely with [name] for review and feedback through a Dropbox embedded within the web page. Participants retrieve feedback via the website when logging back into their account. The personal health coach will not deliver problem-solving content. All content is scripted on the website. Each week for 18-weeks, participants are asked to log on at least once for a total of 1 hour to complete the weekly problem-solving training for that week. The training would include completing workbook pages and submitting responses to the coach. Participants in both groups will receive \$50 in gift cards (\$10 at first session, \$20 at completion of the 9 weeks, then \$20 at 3-month follow-up. Surveys will be administered that are suited to measure diabetes self-care behaviors, dietary patterns, diabetes and CVD knowledge, and barriers to problem-solving for specific health behaviors. Diabetes Self-management behaviors will be measured by SDSCA. Dietary habits will be measured by STCFFS. Problem-solving ability for related health problems will be measured by HPSS.
3. The initial HbA1c reading to check study eligibility would be a routine test performed at the clinic (chart audit). It is also possible if a study participant had a recent HbA1c reading the study could use this as well.

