3. Social risk There are no known risks of subjects participating in a web-based study. Previous studies have successfully conducted web-based interventions and maintained confidentiality of subjects.⁵⁹⁻⁶⁰ To minimize potential issues with confidentiality subjects will receive a secure password protected login for the duration of the 18-week web-based portion of this study. All communication via the Internet will take place across a secure server. Medical chart data will be collected in person by the PI from a designated medical staff person at the participating clinic.

A potential risk of participating in the study is a breach of confidentiality and loss of privacy. To further address privacy, as well as to ensure confidentiality, the investigators will ensure the following measures are taken. All data obtained in the study will be kept confidential. The only parties having access to the data in the proposed study will be the Principal Investigator ([name]), Mentor ([name]) and appropriate research staff, and the KUSM-W Human Subjects Committee.

Hardcopies of completed subject questionnaires will be locked in a secure file cabinet in the PI's office. Responses to the surveys and the clinical/treatment/surveillance information obtained from the EHR will be maintained on the KUSM-W REDCap database. Only the necessary members of the research team will have access to the REDCap database. After a member of the research team initially enters the data, an additional member will review the data and identify errors. A log will be kept of all data collection and analysis steps completed for each subject. For the task analysis and usability testing, a research log will be kept by the research technician regarding steps completed and any errors detected.

Participants in the intervention group are asked to input their HbA1c number on the eDECIDE website. They will also be asked to create a unique username and password to login and use the eDECIDE website. All stored data will be secure and encrypted. Website is in development.

4. Economic risk There are no known economic risks of subjects participating in a web-based study.
5. Potential benefit of participating in the study

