7. Sustainability: No current plan. No partnership currently exist.

K. Personnel who will conduct the study, including:

1. Indicate, by title, who will be present during study procedure(s): [name], Study PI
2. Primary responsibility for the following activities, for example:
 - a. Determining eligibility: Research Assistant/ Principle Investigator
 - b. Obtaining informed consent: Research Assistant/ Principle Investigator
 - c. Providing on-going information to the study sponsor and the IRB: Research Assistant/ Principle Investigator
 - d. Maintaining participant's research records: Research Assistant/ Principle Investigator
 - e. Completing physical examination: Research Assistant/ Principle Investigator
 - f. Taking vital signs, height, weight: N/A
 - g. Drawing / collecting laboratory specimens: N/A- contracting out to a 3rd party
 - h. Performing / conducting tests, procedures, interventions, questionnaires: Research Assistant/ Principle Investigator
 - i. Completing study data forms: Research Assistant/ Principle Investigator
 - j. Managing study database: Research Assistant/ Principle Investigator

L. Assessment of Subject Safety and Development of a Data and Safety Monitoring Plan

1. Elements of the plan include:
 - a. Persons/groups who will review the data (study team; independent safety monitor, data monitoring committee or formal DSMB) Study team
 - b. Data/events that will be reviewed Timeline for data collection points, REDCap data entry process and logon's to eDECIDE website
 - c. Frequency of review: Will review daily/weekly and as needed to maintain study schedule
 - d. Types of analyses to be performed: Will run basic statistics or log entry to see how often participants log on to website. Will monitor computer security to ensure participant's confidentiality remains in take per HIPPA guidelines.
 - e. Safety-related triggers that would cause the PI to stop or alter the study Any breach in confidentiality based on the website

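### Nothing in the plan stops unblinded staff who deliver an intervention from also administering the self-report questionnaires, which leaves those secondary endpoints open to avoidable assessor-related bias

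*Combined protocol and SAP*

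**What the plan says.** **Who assesses.** The personnel list in II.K.2.h reads "Performing / conducting tests, procedures, interventions, questionnaires: Research Assistant/ Principle Investigator". Item i of the same list reads "Completing study data forms: Research Assistant/ Principle Investigator", and item j gives the same two roles the database. II.K.1 names only the investigator as present during study procedures.

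**Blinding.** II.C.1: "Participants and research staff will be aware of random group assignment".

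**Who delivers.** The sections do not agree.
- II.B has eDECIDE participants submit "completed workbook homework to their personal health coach (PI: [name", so the investigator is the coach. Of the control arm it says: "Traditional DECIDE consists of the regular 18-week in-person group sessions led by the candidate, as facilitator".
- II.E.2 refers instead to a "personal health coach (who will be hired for the RCT and work closely with [name] for review and feedback", and describes the control arm as nine in-person group sessions.
- The timeline in II.E.5 lists the control sessions as self-directed on paper and mentions no facilitator.
- II.B and II.E.2 agree that the coach's part is limited: "The personal health coach will not deliver problem-solving content".

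**How questionnaires are taken.** The II.E.5 timeline marks them as virtual at baseline, post-intervention and 3 months. It does not say whether they are self-completed or led by an interviewer. II.F.3 describes hardcopies stored in the investigator's office and staff entry: "After a member of the research team initially enters the data, an additional member will review the data and identify errors".

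**What they measure.** II.C and V.B list diet, self-management behaviour, diabetes and cardiovascular knowledge, and health problem solving as secondary outcomes. The secondary hypothesis in I.A is comparable improvement in the two arms.

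**The concern.** People tend to describe their diet, self-care and problem solving more favourably to someone who has been helping them with those things. If the person who collects the answers has also coached or taught the participant, the score mixes behaviour with that relationship.

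This would matter less if the relationship were the same in both arms. It is not, on any reading of the plan. One arm has written web feedback from a coach. The other has either in-person groups or paper self-study. Pressure to report favourably therefore need not cancel.

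A shift of this kind arises after randomisation and after baseline, so neither randomisation nor baseline adjustment removes it, and a larger sample does not shrink it. Because the hypothesis is comparability, both directions matter: a shift can produce a spurious difference or mask a real one.

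**Working it through.** **Step 1. Does the plan separate delivery from assessment?**

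| Question | Where | Answer in the text |
|---|---|---|
| Who conducts interventions? | II.K.2.h | Research assistant / investigator |
| Who conducts questionnaires? | II.K.2.h | The same two roles, split not stated |
| Do they know allocation? | II.C.1 | Yes |
| Who coaches eDECIDE? | II.B; II.E.2 | The investigator; or a hired coach |
| How is control delivered? | II.B and II.E.2; II.E.5 | In person, in groups; or self-directed on paper |
| Self-completed or interviewer-led? | II.E.5 | Virtual; otherwise not stated |
| Who enters responses? | II.F.3 | A team member, checked by a second; neither said to be blinded |
| Any rule keeping a coach or facilitator away from assessment? | Nowhere | None |

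The overlap in II.K.2.h stands whichever account of the coach and the control arm is right.

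**Step 2. Which endpoints are exposed?** Self-care, diet and problem solving are self-described. Knowledge is scored against correct answers and is less open to favourable reporting. HbA1c and cholesterol come from laboratory tests (II.E.1), and staff receive only a report (II.E.4), so they are outside this point.

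**Step 3. The plan's sample size.** The only sizing statement, in II.C, concerns HbA1c: difference 1%, SD 1.3%, two-sided 5%, 35 per group, 20% attrition, 80% power.
- Evaluable per arm: 35 × (1 − 0.20) = 28.
- Standardised difference: 1 / 1.3 = 0.769.
- Power of the two-sample t-test with 28 per arm: 80.7%. The stated figure reproduces.

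I therefore use 28 per arm as the lower case and 35, with no loss, as the upper.

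**Step 4. Illustration of a differential shift.** The documents give no size for assessor bias. Assume that the arms are truly equal on one questionnaire, that reporting differs between arms by *b* SD, and that an unadjusted two-sample test is used.
- SE of the standardised difference = √(2/n): 0.267 for n = 28 and 0.239 for n = 35.
- Rejection rate ≈ P(|Z + b/SE| > 1.96).

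| b (SD) | n per arm | b/SE | Normal approximation | t-test |
|---|---|---|---|---|
| 0.1 | 28 | 0.37 | 6.6% | 6.6% |
| 0.1 | 35 | 0.42 | 7.0% | 7.0% |
| 0.2 | 28 | 0.75 | 0.113 + 0.003 = 11.6% | 11.4% |
| 0.2 | 35 | 0.84 | 0.131 + 0.003 = 13.3% | 13.1% |

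The nominal rate is 5%.

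**Step 5. The opposite error.** The same shift can act against a real difference. A true difference of 0.2 SD with an opposing shift of 0.2 SD has an expected observed difference of 0.2 − 0.2 = 0. For a comparability hypothesis this error is at least as relevant.

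**The case against.** A reader might infer that one investigator coaches the eDECIDE arm, leads the control arm and then asks both groups the questions. The documents do not support that.
- II.B gives the control sessions to the candidate, and no section says outright that the candidate is the investigator.
- II.E.2 says the coach will be hired, and II.E.5 shows no facilitator for control. On those two sections the investigator neither coaches nor leads.
- The slash in II.K.2.h allows the research assistant to handle every questionnaire. II.K.1 cannot be literal for every procedure, since blood draws are contracted out.
- Virtual questionnaires may already be self-completed, in which case contact with an assessor would be small.

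Other points on that side also have force. Staff transcription of answers already given is a different mechanism from a wish to please the assessor, and a second team member checks it. The II.F.3 text may be carried over, because it still describes logs for the task analysis and usability testing that I.C places in previous phases. If one person dealt with both arms, some of the bias could cancel. This is also an open-label pilot, and the endpoints at issue are secondary.

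These arguments make the bias possible rather than established, in both size and direction. They do not close the gap. Nothing requires the research assistant to do the assessments, the same line gives that role intervention duties too, and the mode of completion is never stated.

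**Conclusion.** The concern holds in a limited form. As written, the plan permits an unblinded person who delivers an intervention to collect the self-report endpoints, and it does not fix the mode of completion. II.B, II.E.2 and II.E.5 conflict on who coaches and on how control is delivered, and must be reconciled. Self-care, diet and problem-solving results, and knowledge results less so, are open to an avoidable bias that could create or hide a difference.

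The figure of about 7% to 13% rejection, against a nominal 5%, rests entirely on the assumed shift of 0.1 to 0.2 SD and on 28 to 35 per arm. It illustrates scale and does not estimate what will happen in this trial. The primary outcome and the lipids are not affected. This is a cheap improvement to the secondary endpoints and does not threaten the trial's main result.

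**What to change.** **Change.**
- State that at baseline, week 18 and 3 months participants complete the questionnaires themselves through an individual REDCap survey link.
- State that no one who coaches, facilitates or otherwise delivers either intervention is present or on the call.
- Limit help to scripted technical support from a team member with no delivery role. A research assistant who delivers any part of an intervention is barred as well.
- Amend II.K.2.h to match, and replace staff entry of survey responses (II.F.3) with direct capture.
- Reconcile II.B, II.E.2 and II.E.5 on the coach and the control delivery.
- State as a limitation that participants know their own arm, so some reporting bias remains. Because IV.A gives the study team named access to REDCap, participants may also expect their answers to be seen.

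**Cost.** Protocol wording and survey set-up. The tools are already in the plan: virtual questionnaires (II.E.5), REDCap for e-consent (III.C) and daily Internet access at home or in a private location as an eligibility condition (II.D.1). No extra staff are needed if one existing team member is kept out of delivery.

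**Downside.** Some items may be skipped when no interviewer is present. Required-item prompts limit this. So would email and text reminders, but II.E.5 plans those only for the sessions, so they must be extended to the questionnaire visits.

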APPENDIX I: VULNERABLE POPULATIONS

- I. Groups below are not part of the active recruitment pool or target groups

- II. Cognitively or decisional impaired individuals:** Those with cognitive or decisional impairment will not be eligible for the study.
- III. Children:** Children will not be eligible for the study.
- IV. Pregnant women:** Women who are currently pregnant or have gestational diabetes will not be eligible for this study.
- V. Prisoners:** Prisoners are not an eligible population for this study.
- VI. Students and/or Employees:** This is a community recruitment effort. KUMC Students and Employees will not be recruited for this study.
